Stroke is a leading cause of disability in the US. Most stroke survivors have difficulty performing daily activities and participating in the community. Efficacy of interventions that address the chronic needs of stroke survivors has been identified as a high priority for stroke research. A gap in care exists at the point of transition from inpatient rehabilitation (IR) to home, when survivors encounter new environmental barriers due to the cognitive and sensorimotor sequelae of stroke. Resolving these barriers and improving independence in the community have potential to significantly improve stroke survivors' long-term morbidity. The proposed study investigates the efficacy and safety of a novel, enhanced rehabilitation transition program to reduce environmental barriers and improve daily activity performance and community participation. Community Participation Transition after Stroke (COMPASS) uses two complementary evidence-based interventions: home modifications and strategy training delivered in the home. Home modifications provide environmental support to compensate for impairments. Strategy training enables patients to identify and prioritize ADL problems, identify barriers to performance, and develop strategies to resolve barriers. The complementary effects of these therapies at a novel point of care offer a robust intervention for a current service gap. The primary aim of this phase IIb, single-blind, parallel-group, randomized controlled trial is to investigate the efficacy of COMPASS during the transition from IR to home. Participants will be randomized to receive either COMPASS or attentional control. We hypothesize that COMPASS participants will demonstrate significant improvements in community participation and ADL performance and a significant reduction in environmental barriers versus control. In preparation for a phase III multicenter trial, we will explore additional candidate study endpoints and establish intervention safety by examining the rates of falls and hospital readmissions. Finally, we will conduct a process evaluation examining outcomes such as reach, cost, fidelity, and adherence to aid interpretability of the trial and implementation. The aims fill critical gaps in stroke rehabilitation evidence by investigating the efficacy, safety, and implementation of an intervention targeting the transition from an acute to a chronic condition. The results of this trial will provide important information about the long-term participation and environmental barriers of stroke survivors. The project has the potential to resolve the significant unmet need of disability after stroke.

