NIH Toolbox Instrumental Support Scale measures the availability of support for an individual to assist with completing daily tasks; 8-item scale, uses a 5-point likert scale response, scores are summed with higher score indicating more instrumental support.

10-Item Connor-Davidson Resilience Scale will measure resilience or ability to adjust to a stressful situation; consists of 10 items, all answered used a 5-point likert scale; total scores range from 0-40, with higher scores indicating greater resilience.

Healthcare Utilization and Mortality

Retrospective review of the medical records of all randomized participants to collect date of death, hospitalizations, emergency room visits, and skilled nursing facility (SNF)/Inpatient Rehabilitation (IPR) admissions between participants' date of enrollment until date of final study contact as a follow up metric to identify patient outcomes (see waiver of consent).

Statistical Analyses

Intention-to-Treat Analysis

We will perform our analyses using an intention-to-treat paradigm. We will perform exploratory data analysis looking for extreme or otherwise unusual values. Non-normal and heteroscedastic data will be transformed as necessary.

Baseline Analyses

We will use unpaired *t* tests and chi-square tests to compare T0 and baseline characteristics in the two groups for descriptive information (except when statistical assumptions are not met, in which case we may use Wilcoxon or Fisher exact tests).

Missing Data

We expect missing values in outcome measures because of dropout, death, missed assessment, or nonresponse. Our main analysis, a linear mixed-effects model, accommodates missingness due to treatment, prior outcome, or baseline covariates missing at random.⁸² Assuming that missing data occur at random, inferences will be valid even if we have differential dropout by intervention arm. If the missing data mechanism is not ignorable (ie, missing is not at random), then mixed-effects selection models or pattern-mixture models will be used.⁸³

Primary Analysis

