For the secondary analyses of the change in SIS score at 1 year and the change in I-HOPE at 1 year, we will use the same approach as for the primary analysis because these two outcomes are also continuous. We have overall type I error control for testing the 1-year change in these three analyses at the design stage. The significance level for testing is 0.016. In addition to comparison of 1-year change, we will extend the model by including scores immediately after intervention and at 6 months to see whether the difference in outcomes is achieved at those time points. Depending on the form of time variable in the model, we will use appropriate regression coefficients or a linear combination of the regression coefficients to determine the difference in change of these scores between arms at certain time points. Interpretation of these results should be cautious because we do not have the type I error controlled for these analyses. Because it is possible that severity of functional impairment after stroke may impact response to treatment, we will analyze impact of functional impairment on response to treatment. We will examine functional impairment by group interaction to examine possible differential intervention effects of functional impairment on community participation and performance of daily activities.

Safety

To determine whether the intervention poses no greater risk than AC, we will examine the differences in numbers of falls and rehospitalizations between groups. The statistical models for count data will be used for analyses of these two outcomes. Using the number of falls as an example, we will fit a Poisson regression model (with overdispersion adjustment if necessary), in which a dummy variable for the intervention arm is used. The regression parameter estimate for this dummy variable is the log of rate ratio of falls for COMPASS versus control arm, and exponentiation of the regression parameter estimate is rate ratio. Using the parameter estimate and its standard error, we can construct a two-sided 95% CI for the rate ratio. We expect the confidence interval for rate ratio will include 1, indicating no significant difference in the fall rate between the two groups.

Process Outcomes

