Evaluate acceptability and feasibility to aid in the interpretability of the trial. COMPASS will have high acceptability (80% retention), high fidelity by therapists (95% of elements and 90% of dose delivered), low safety risk (no increased rate of falls or health care use compared with the AC group), and high adherence (80% of modifications in use) at 12 months. We will conduct between-group comparisons of process endpoints collected at each time point (time to first fall, number of injurious falls, health care utilization rate, dosage delivered, and adherence rate) using unpaired *t* tests or chi-square tests. We will compare the characteristics of patients who complete the assigned intervention with those who do not for differences in stroke severity and comorbidities. Descriptive statistics will be used for costs per participant and adherence.

Sample Size Calculations

The study is designed to have 80% of power to reject three null hypotheses of equal mean changes in the primary and secondary endpoints (RNLI, SIS, and I-HOPE) using a two-sided, two-sample, unequal-variance *t* test with overall type I error <0.05 . Three alternative mean changes (standard deviation [SD] of change) in intervention and control populations are 15.3 (SD 22.6) versus 1.3 (SD 23.4) for RNLI, 15.7 (SD 16.1) versus 5.6 (SD 9.1) for the SIS ADL domain, and 62.1 (SD 26.1) versus 46.2 (SD 18.8) for I-HOPE. With a 1:1 allocation ratio, 130 patients (65 in each group) are needed for the RNLI outcome, 84 are needed for the SIS outcome, and 100 are needed for the I-HOPE outcome. We will enroll 180 patients to account for a 30% attrition rate. This magnitude of between-group difference is considered clinically meaningful based on prior relevant literature and is achievable based on our pilot study. Sample size calculation includes correlation between baseline and follow-up measures and is based on analysis of change scores, which is equivalent in efficiency to the proposed analytic model. Based on the number of stroke patient participants, we will enroll an equivalent number of caregivers.

Strengths and Limitations

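### No comparison of deaths by arm is planned, so the written safety criterion can be met despite an excess of deaths

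*Combined protocol and SAP*

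**What the plan says.** Confirming the safety of COMPASS is part of Specific Aim 2. Three places in the combined protocol and SAP say how this will be done.

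- Abstract: the trial will "establish intervention safety by examining the rates of falls and hospital readmissions".
- Statistical Analyses, Safety: to judge whether COMPASS carries more risk than attention control, "we will examine the differences in numbers of falls and rehospitalizations between groups". For falls, the worked example, "we will fit a Poisson regression model (with overdispersion adjustment if necessary), in which a dummy variable for the intervention arm is used". The anticipated result is stated too: "We expect the confidence interval for rate ratio will include 1, indicating no significant difference in the fall rate between the two groups".
- Statistical Analyses, Process Outcomes: COMPASS is expected to show "low safety risk (no increased rate of falls or health care use compared with the AC group". The process endpoints compared between groups are "time to first fall, number of injurious falls, health care utilization rate, dosage delivered, and adherence rate".

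Deaths are captured elsewhere. Healthcare Utilization and Mortality provides for "Retrospective review of the medical records of all randomized participants to collect date of death, hospitalizations, emergency room visits" and facility admissions. The version 8.3 entry under Version Updates gives safety monitoring as one purpose of this chart review. Adverse Event Reporting and Safety Monitoring requires each death to be reported at once to the human research protection office. In the Statistical Analyses section, death appears only under Missing Data, as one reason why outcome values may be absent.

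**The concern.** The plan undertakes to confirm safety in stroke patients aged 50 or over, in preparation for a phase III trial. It collects the most serious safety outcome and then gives it no place in the safety analysis. The chart review was added in 2023 partly for safety, but the Safety section was not extended to use the dates of death that it yields. A report that follows the plan could conclude that COMPASS poses no added risk without stating how many participants died in each arm. A phase III team relying on that conclusion would not know whether deaths had been balanced.

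**Working it through.** The point rests on the text. The plan states no mortality rate, safety margin or safety power, so there is no figure of its own to reproduce.

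**Step 1. Which outcomes enter the safety conclusion?**

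| Section | Outcomes compared by arm | Death included? |
|---|---|---|
| Abstract | falls, readmissions | no |
| Safety | falls, rehospitalizations | no |
| Process Outcomes, low-risk statement | falls, health care use | no |
| Process Outcomes, endpoint list | time to first fall, injurious falls, utilization, dosage, adherence | no |

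**Step 2. Where do deaths appear?** In the chart review (collection), in adverse event reporting (case by case) and under Missing Data (a cause of absent values). None of these is a comparison by arm. It follows that no number of deaths in either arm can by itself make the written criterion fail.

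**Step 3. How complete is the source?** The collection statement covers all randomized participants. The waiver section (Retrospective Chart Review) limits the search to one health system's records, from enrollment to final study contact. Deaths recorded elsewhere, or after the last contact, could be missed if charts were the only source.

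**Step 4. What would a comparison show?** Input from the documents: 180 participants allocated 1:1, so 90 per arm. Assumed for illustration: 9 COMPASS deaths and 4 control deaths.

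- Risks: 9/90 = 10.0% and 4/90 = 4.4%. Risk difference = 5/90 = 5.6 points; Newcombe 95% CI -2.4 to 13.9.
- Risk ratio = 9/4 = 2.25. SE of log ratio = √(1/9 - 1/90 + 1/4 - 1/90) = √0.3389 = 0.582. 95% CI = 2.25 ÷ and × exp(1.96 × 0.582) = 0.72 to 7.04.

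A second assumed split, 10 versus 5, gives a risk ratio of 2.0 (0.71 to 5.62).

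**Step 5. Would a test settle the matter?** No. Take 5% versus 10% mortality (assumed) and two-sided 0.05. The standard error is √(2 × 0.075 × 0.925/90) = 0.0393 under the null and √((0.05 × 0.95 + 0.10 × 0.90)/90) = 0.0391 under the alternative. Power = Φ((0.05 - 1.96 × 0.0393)/0.0391) = Φ(-0.69), about 25%. With 5 control deaths, Fisher's exact test needs at least 14 COMPASS deaths for p < 0.05. The useful output is an estimate with its interval, not a pass or fail.

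**Step 6. Do deaths distort the fall and readmission counts?** Only slightly. The Safety section states no person-time term. Assume equal true event rates and deaths spread evenly over the year. Mean time at risk is then 1 - d/2 for mortality d. For 10% versus 5%, the apparent ratio is 0.95/0.975 = 0.974; for 15% versus 5%, it is 0.925/0.975 = 0.949. A person-time offset removes this.

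For readmissions the direction is not fixed. If a share p of deaths brings one extra terminal admission, expected admissions per person are rate × (1 - d/2) + p × d = rate + d × (p - rate/2). More deaths then raise the count whenever p exceeds rate/2: above 25% at 0.5 admissions per year, above 50% at 1.0.

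**The case against.** The strongest reply is that deaths are far from ignored. Each is reported immediately. A serious adverse event that raises participant risk halts the study. A monitoring committee may recommend termination, and Premature Study Termination ends the trial early on significant safety concerns. The low-risk statement sits among expected process results, next to retention and fidelity, and is not a formal decision rule. The intervention is rated minimal risk, and a mortality comparison at this size has little power.

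Most of this is correct, and it limits the point. What it does not supply is an estimate by arm for the safety conclusion: the oversight provisions specify no comparison of deaths between arms. Low power is a reason to show the interval, not a reason to omit the outcome.

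A reader might infer three stronger things that the documents do not support:

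- That safety rests on two counts and nothing else. Process Outcomes adds time to first fall, injurious falls and health care utilization.
- That deaths bias the planned comparisons materially in favour of COMPASS. Step 6 shows a small effect that an offset removes and whose direction for readmissions is uncertain.
- That the falls and rehospitalization tests are defective because they would usually miss a rise in mortality. Tests of other outcomes were never designed to detect it.

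**Conclusion.** The point holds as a gap between collection and analysis. Dates of death are gathered and deaths are reported, yet the safety conclusion is drawn from falls, rehospitalizations and health care use, with no comparison of deaths by arm. Followed as written, the criterion can be satisfied despite an excess of deaths. That rests on the text alone.

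Its practical size cannot be derived from the documents. On the assumed 9 versus 4 deaths of 90, a risk ratio of 2.25 with an interval from 0.72 to 7.04 would go unreported in the safety analysis. Such a result would neither show harm nor exclude it, and a reader of a safety claim should see it. The efficacy analyses are not affected. Nor do the documents support reading this as evidence that COMPASS raises mortality, or that a death would go unnoticed during the trial.

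**What to change.** - **Safety:** add all-cause death by arm among all randomized participants as a safety outcome. Report counts, risk difference and risk ratio with 95% CI. Combine serious adverse event reports, study contacts and chart review, and state that chart review covers one health system up to final study contact.
- **Abstract and Process Outcomes:** extend the safety wording to include deaths. Quote the interval for deaths in any safety conclusion, and state that a non-significant difference is not evidence of safety.
- **Fall and rehospitalization models:** include time at risk as an offset.
- **Optional:** report time to death or first rehospitalization as a supporting analysis.

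The cost is a change of wording, a short analysis and some reconciliation of death records across sources; no added visits are needed. Completeness will depend on those sources, because charts alone may miss deaths. The interval will be wide, so the safety statement becomes more cautious. The change is best made before results by arm are seen.

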6/14/2018	3.0	Changed time points caregivers are assessed
10/18/18	4.0	Added transportation option to home visit as staff vehicle. This has been ok'd by Wash U insurance group
11/30/18	5.0	If a person has an extended hospital stay or goes to a SNF for the short term, we will push back their T3 based on the extra days of stay. Normal LOS is considered 3 days.
3/8/19	6.0	Changed our n to 180, based on retention rates
1/2/20	7.0	Decided if T3 is missed by more than 3 months, we will skip T3 and go to T4
3/31/20	7.1	Because of the stay-at-home orders our primary endpoint will be impacted (community participation). In addition, because we can't go into people's homes, we will need to do follow up via phone and won't be able to do the I-HOPE barriers. We will add repeat of the follow-up time points to collect data in the home when we can go back in. Those timepoints will be T2COVID, booster 1&2COVID,T3COVID, T4COVID. At this point, those are 60 days after their original time point (30 days for SAH orders and 30 more days to allow the person to get back into the community after the SAH orders are lifted).
4/1/20	7.2	We will ask our participants if they have access to technology needed for telehealth and are willing to participate in visits remotely using telehealth.
4/9/20	7.3	In order to better understand the impact the COVID-19 pandemic is having on our participants, we will add additional measures to ask all participants, both those who have finished and those are still in follow up. Measures will include: RNLI, SIS, GDS, PROMIS SF Anxiety, NIH Instrumental Support, Pittsburgh Sleep Quality Index, PROMIS SF Social Isolation, 3-Item UCLA Loneliness Scale, and the Connor Davidson Resilience Scale.
6/26/20	7.4	In order to reduce physical contact with participants during the COVID-19 pandemic, we will switch to electronic consenting when at all possible.
7/10/20	7.5	Added that we will continue with e-consenting even after COVID-19 is over
11/11/20	8.0	Added the option for modified assessment process during COVID when participant is not able to leave TRISL for home assessment.
1/6/22	8.1	Added question about participants' COVID-19 vaccination status.
6/22/2023	8.2	Updated contact information for study personnel
8/28/23	8.3	Added statement about waiver of consent to collect chart review data as a follow up metric to identify patient outcomes and for safety monitoring.

World Health Organization Data Set

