For participants who experience a delay in the study timeline (such as hospital admission, travel, short-term admission to a skilled nursing facility, etc.), the timeline will be adjusted accordingly. For example, if someone returns to the hospital during the intervention period and is in the hospital for 4 weeks, their T2 follow-up will be pushed back 4 weeks. If we can't schedule the T3 for three months past the normal time point for the T3, we will skip the T3 and schedule the T4.

Our primary outcome of the study is community participation. This has been severely limited by the current COVID-19 pandemic stay-at-home orders. We will adjust some of our follow up timepoints for data collection to reflect the SAH orders and allow people a chance to get back into the community before collecting community participation data. Our original timepoints are as follows: T2 (immediate post treatment), T3 (six months post stroke) and T4 (12 months post stroke). We will collect data at those timepoints but we are adding an additional collection time for each of those. Our T2COVID, T3COVID, T4COVID are all 60 days after the original T2/T3/T4 time point to allow for the SAH orders to lift and the participant to resume normal community participation. We will adjust these timepoints if the SAH orders continue longer than anticipated at this point.

Waiver of Consent: Retrospective Chart Review

At this time, we have consent to review medical charts during the enrollment and treatment process. However, we do not have permission to review the record after treatment was completed. Because we have ceased recruiting and all of our participants are finished with their participation in the study intervention and control groups, we no longer have contact with the majority of study participants. We would like to review medical charts (Wash U BJH medical records only) from participants who signed the Wash U COMPASS II consent form. We will collect limited data points, including date of death, hospitalizations, emergency room visits, and SNF/IPR admissions between their date of enrollment in this study and date of final study contact. For the waiver of consent, we will recruit participants already enrolled in this study.

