The data collected from this retrospective chart review will be saved in Excel as a limited dataset (with no direct identifiers) on Box in a folder only accessible to the research team and separate from the full REDCap database) to protect the participant's information from a breach of confidentiality. The results of the research will not affect the clinical care of the individuals because the information is being collected retrospectively after the participant's completion of the study intervention.

Adherence to the conditions required for an IRB Waiver of Consent are as follows:

- 1) **The research involves minimal risk**, as the review of the participant's medical records is for limited information. The likelihood of any adverse effects on the subject's status, employment, or insurability is exceedingly low. Stringent measures have been implemented to restrict the record review to specific data to minimize the risk of a breach of confidentiality. One research team member trained in EPIC and

HIPAA compliance will access medical records and will only search for and document the above mentioned data. A limited dataset including only an ID number, stroke date, rehab discharge date, date of last visit/last study contact, and dates of death, hospitalization, ER visit, and SNF admission will be saved in an Excel file separate from the REDCap database which contains full study data. No direct identifiers such as names, birth dates, address, phone numbers etc will be saved in this Excel file. Only research team members will have access to look up the ID number in REDCap to view other research data. The Excel file will be stored on a Box folder only accessible by the study team. Data will be retained for six years following project close-out and then will be destroyed. It should be noted that reaching out to subjects for their consent may potentially be seen as an intrusion on their privacy and could lead to undue anxiety or emotional pain amongst participants or their families.

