- 2) **The rights and welfare of the individual would not be adversely affected** because the indicated events have already occurred and been documented in the patient's medical record regardless of the research. The retrospective review of this information takes place after the participant's involvement in the study intervention and therefore does not have any bearing on treatment decisions. Therefore, participants are not denied standard care they are entitled to receive under any circumstances.
- 3) **The research could not be practicably carried out without a waiver.** Due to the retrospective nature of this data collection, it is not possible to contact all study participants for a complete review of these variables as a follow-up metric. Some participants may be uncontactable due to death, institutionalization, or changes in cognitive status after completing the study intervention.
- 4) **It would not be appropriate to provide these subjects with information about the results of the research** as the results would have no effect on the participants. The events have already occurred for the participants and they are aware of their occurrence independent of the study. There is no anticipated benefit to the participants that would alter what has already taken place.

Participants who are still enrolled will be re-consented.

Data Collection

Outcome Assessments for Baseline & Follow-up Home Visits

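### The chart review of death and health-care use stops at each participant's last study contact, so follow-up is unequal and may end because of the events being counted

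*Combined protocol and SAP*

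**What the plan says.** The Waiver of Consent section limits the chart review to a few items, "including date of death, hospitalizations, emergency room visits, and SNF/IPR admissions between their date of enrollment in this study and date of final study contact". Healthcare Utilization and Mortality, under Data Collection, applies the review to everyone randomized and keeps the same end point: "date of enrollment until date of final study contact as a follow up metric to identify patient outcomes". The first waiver condition lists the fields to be stored, among them "date of last visit/last study contact, and dates of death, hospitalization, ER visit, and SNF admission"; it sets no end date of its own and refers back to the items already named. The Version Updates entry for 8/28/23 gives the purpose: "as a follow up metric to identify patient outcomes and for safety monitoring". The third waiver condition explains why fresh consent is impracticable: "Some participants may be uncontactable due to death, institutionalization, or changes in cognitive status after completing the study intervention". The source is "Wash U BJH medical records only".

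Elsewhere, the Follow-up Period section places T4 at 12 months after stroke, collects falls and health-care use by monthly automated call, lets the timeline slip after delays, and adds a T4COVID assessment 60 days after T4. The Safety section compares counts of falls and rehospitalizations in a Poisson model with an arm indicator and mentions no person-time offset. Process Outcomes sets a 12-month criterion of "no increased rate of falls or health care use compared with the AC group". Final study contact is not defined, and no section gives the chart review a common end date.

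**The concern.** A chart review is useful for safety because it can see what happened to people the study team could no longer reach. Here it closes on the day the team last reached them. Death, admission to a nursing facility and serious rehospitalization are all reasons contact stops, so the length of observation can depend on the outcome being observed. The monthly calls do not fill the gap, because they stop when contact stops.

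The window also varies in the other direction. A participant whose T4 was delayed, who had a T4COVID assessment, or who was telephoned for the pandemic measures after finishing may have a final contact later than 12 months.

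At stake is whether the chart-based figures for mortality and health-care use can be compared between arms over the 12-month horizon on which the plan judges safety, in a trial meant to establish safety ahead of a phase III study.

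**Working it through.** **Who is covered under the wording as it stands**

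- Completes T4 on time: full planned coverage.
- Admitted to hospital or a nursing facility and then resumes: the stay is inside the window, because later contact follows it.
- Admitted and never reached again: events before the last contact are kept; later ones, possibly including the admission that ended contact, are not.
- Dies before T4: if final contact means contact with the participant, the death necessarily comes after it and is outside. If a caregiver's report of the death counts as the final contact, the death is inside. The text does not settle which.
- T4 delayed, or T4COVID done: the window runs past 12 months, by 60 days when T4 is on time and T4COVID follows as planned.

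**Figures available.** The documents give no number for the chart review. The related inputs, in Sample Size Calculations and Process Outcomes, are 180 enrolled, a 30% attrition allowance, and an 80% retention target (20% not retained). The allowance does not quite reproduce: 130 / (1 − 0.30) = 185.7, so 186 rather than 180, and 1 − 130/180 = 27.8%. That gap does not bear on this point. Neither percentage is a measured rate of lost contact; both serve only as a plausible range.

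**Person-time outside the window.** Take 12 months per participant, ignoring the gap between stroke and enrollment and any censoring at death: 180 × 1 = 180 person-years. Time outside = 180 × a × (1 − f), where a is the share losing contact before 12 months and f is the mean fraction of the year observed in those people. The values of f are assumptions.

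| a | f | Person-years outside | Share of 180 |
|---|---|---|---|
| 20% (36 people) | 75% | 36 × 0.25 = 9 | 5% |
| 20% | 50% | 36 × 0.50 = 18 | 10% |
| 20% | 25% | 36 × 0.75 = 27 | 15% |
| 30% (54 people) | 75% | 54 × 0.25 = 13.5 | 7.5% |
| 30% | 50% | 54 × 0.50 = 27 | 15% |
| 30% | 25% | 54 × 0.75 = 40.5 | 22.5% |

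**Events missed.** If the event rate after loss of contact is k times the rate before it (assumption), and 15% of time is outside, the share missed is 0.15k / (0.15k + 0.85):

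- k = 1: 15%
- k = 2: 0.30 / 1.15 = 26%
- k = 3: 0.45 / 1.30 = 35%

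**Comparison of arms.** Suppose the true rates are equal and constant, and counts are compared without person-time.

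- Equal loss in both arms: ratio 1.0, whatever the amount.
- Loss of 40% versus 20% (assumption), f = 50%: (1 − 0.40 × 0.50) / (1 − 0.20 × 0.50) = 0.80 / 0.90 = 0.89.
- The same with f = 25%: (1 − 0.40 × 0.75) / (1 − 0.20 × 0.75) = 0.70 / 0.85 = 0.82.

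An offset for observed time returns these last two ratios to 1.0. It does not help where the rate rises after loss. With 40% versus 20% lost, f = 50% and k = 2, the ratio over the full year is (0.80 + 0.20 × 2) / (0.90 + 0.10 × 2) = 1.20 / 1.10 = 1.09, while the offset analysis of observed time still gives 1.0. So the window needs changing as well as the model.

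**The case against.** Much can be said for the plan.

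A reader might infer that mortality must come out near zero in both arms. The documents do not support that. Final contact is undefined, caregivers are enrolled and assessed at follow-up, and the dataset has a field for dates of death, so the authors evidently expected to record some. Deaths must also be reported immediately to the HRPO under Adverse Event Reporting, and death is not a named endpoint in the Safety section. What remains is that two abstractors could obtain different death counts from the same charts.

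A reader might also infer that the safety objective as a whole rests on truncated data. Falls are not chart-review items; the prospective source for falls and health-care use is the monthly calls; and no section says that the Poisson model or the 12-month criterion will use chart data. The point therefore covers the chart-based comparison only.

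Nor are all events of people lost to follow-up dropped: those before the last contact are kept, and the charts can recover events missed by unanswered calls up to that date. The third waiver condition explains why consent cannot be sought; it does not say that the review exists to count events after contact ended.

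Finally, a reader might infer that the arm with more deaths or institutionalizations will look safer. No differential loss is documented, the plan describes its estimate as a rate ratio (so person-time may be intended), and equal, similar loss leaves the ratio unbiased. The direction of any bias is unknown.

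These points reduce the size of the problem. None supplies a common end date or brings back events after loss of contact.

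**Conclusion.** The point stands as a cheap improvement to a secondary data source. It is not a flaw in the primary or secondary efficacy analyses. As written, chart follow-up for death, hospitalization, emergency visits and nursing or rehabilitation admissions is unequal between participants and possibly informative. About 5% to 22.5% of 12-month person-time would lie outside the window if 20% to 30% lose contact after 25% to 75% of the year. That range is illustrative: the percentages come from a retention target and a sample-size allowance, and the timing is assumed. The recoverable part is smaller, since no one is at risk after death and records are closed after withdrawal of access, although a death itself would be captured. Bias between arms requires that the loss, or the event rate after it, differ by arm.

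**What to change.** In the Waiver of Consent section, replace the span "between their date of enrollment in this study and date of final study contact" with a common window from randomization to 12 months after stroke for every participant covered by the waiver, whatever the date of last contact, censored only at death or at withdrawal of record access. Make the same change in Healthcare Utilization and Mortality. Report deaths and health-care use by arm on that window, with person-time as an offset in the count models. Events seen after 12 months in delayed participants can be listed separately.

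Cost: one sentence in each of two places, an IRB amendment allowing records to be read after the last contact, and some additional reading by the same abstractor in the same charts. Stroke, event and death dates are already in the planned dataset. The IRB may decline, and people who withdraw access stay excluded. The restriction to one health system's records remains, so events treated elsewhere will still be missed and the report should say so.
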